4.11.4 Vital Signs

Vital signs will be performed as shown in [Table 6-1](#). The following vital signs measurements will be obtained:

- Supine Systolic blood pressure (SBP) [mmHg].
- Supine Diastolic blood pressure (DBP) [mmHg].
- Supine Heart rate (beats per minute [bpm])
- Pulse rate (bpm).
- Tympanic (ear) Body temperature [°C].

Vital signs data will be listed by subject including changes from baseline. The baseline for the vital signs measurements will be the measurement on Day -1.

Descriptive statistics (n, mean, SD, median, minimum, maximum) for absolute values and changes from baseline will be summarized descriptively in tabular format by time of collection and by treatment group.

4.11.5 12-Lead Electrocardiogram (ECG)

Standard safety 12-lead ECGs will be performed as shown in [Table 6-1](#).

The following ECG parameters will be recorded:

- PR interval (msec)
- QRS interval (msec)
- QT interval (msec)
- QTc interval (msec)
- QT interval corrected using the Fridericia correction formula (QTcF) (msec).
- HR (beats per minute [bpm]).

The ECG will be evaluated by the Investigator as ‘Normal’, ‘Abnormal, Not clinically significant (NCS)’ or ‘Abnormal, CS’.

All ECG parameters will be listed by participant for each treatment group and time point including changes from baseline.

Baseline is defined in section [4.2.4](#).

Descriptive statistics for absolute values and changes from baseline will be presented by treatment group. A categorical QTc analysis will also be performed.

Measurements obtained at Screening and EOS will not be included in the shift tables.

Measurements obtained prior to dosing in each period will be included in the tabulations for the treatment received in that specific treatment period.

4.11.6 12-Lead Holter ECG

A 12-lead Holter ECG recording will be performed for 24 hours on Day -1, Day 10, and Day 16 of each treatment group. The Holter recording will be used to obtain a measurement of mean HR per hour on each day.

Mean HR per hour on Day -1, Day 10, and Day 16 will be summarized (mean, SD, minimum, maximum and median) by time point (each hour) and treatment.

Day -1 measurements will be considered as baseline.

Individual measurements of mean HR per hour will be displayed in a listing including the time-matched changes from baseline from Day -1 to Day 1 and the placebo-corrected time-matched changes and Holter's comment.

4.11.7 Physical Examination

Physical examinations will be performed as shown in [Table 6-1](#).

The full physical examination includes an assessment of general appearance and a review of systems (dermatologic, head, eyes, ears, nose, mouth/throat/neck, thyroid, lymph nodes, respiratory, cardiovascular, gastrointestinal, extremities, musculoskeletal, neurologic systems).

Changes from baseline in any physical examination findings identified by the Investigator as clinically significant must be recorded as an AE on the appropriate eCRF.

Clinically significant physical examination, with respect to number frequencies and percentage, will also be tabulated by time of collection and treatment group. Clinically significant physical examination findings will be listed.

Other safety evaluations of comprehensive skin examination and Fitzpatrick scale will be listed.

[REDACTED]

[REDACTED]

[REDACTED]

[REDACTED]

[REDACTED]

[REDACTED]

4.12.1 Columbia Suicide Severity Rating Scale (C-SSRS)

C-SSRS will be summarized by time of collection and treatment group.

C-SSRS score will be listed.

4.13 Determination of Sample Size

Using a 2-sample t-test with a 1-sided 0.05 significance level, a sample size of 60 evaluable subjects who complete the study (20 subjects in Group 1 receiving SC setmelanotide and 20 subjects each in Groups 2 and 3 receiving SC placebo) will provide at least 85% power to exclude that setmelanotide causes more than a 10 msec QTc effect at clinically relevant plasma levels, as shown by the upper bound of the 2-sided 90% confidence interval (CI) of the model-predicted QTc effect ($\Delta\Delta QTcF$) at the observed geometric mean C_{max} of setmelanotide on Day 10 and Day 16 in the study individually.

To demonstrate assay sensitivity using moxifloxacin with a 1-sided 0.05 significance level, a sample size of 20 evaluable subjects receiving moxifloxacin and 20 evaluable subjects receiving placebo at each ECG assessment day (Days 10 and 16) will provide at least 81% power to demonstrate assay sensitivity with a 1-sided 0.05 significant level. The power to detect the effect of moxifloxacin on QTc over the entire crossover period is at least 86%.

As such, a total of approximately 72 subjects are planned for enrollment to achieve 60 completers, accounting for dropouts.

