To demonstrate assay sensitivity using moxifloxacin with a 1-sided 0.05 significance level, a sample size of 20 evaluable subjects receiving moxifloxacin and 20 evaluable subjects receiving placebo at each Holter ECG assessment day (Days 10 and 16) will provide at least 81% power to demonstrate assay sensitivity with a 1-sided 0.05 significant level. The power to detect the effect of moxifloxacin on QTc over the entire crossover period is at least 86%.

As such, a total of approximately 72 subjects are planned for enrollment to achieve 60 completers, accounting for dropouts.

Inclusion Criteria:

Subjects must meet all of the following criteria to be eligible for study participation:

1. Males or females between 18 and 50 years of age, inclusive.
2. Subject has body mass index (BMI) between 18.0 and 30.0 kg/m², inclusive.
3. Subject is in good health, as confirmed by no clinically significant findings from medical history, physical examination, 12-lead ECG, vital signs measurements, clinical laboratory evaluations, and liver function tests at Screening, Check-in (Day -2) and baseline (Day -1).
4. Female participants of childbearing potential must be confirmed non-pregnant and agree to use contraception. Female participants of non-childbearing potential, defined as: surgically sterile (status post hysterectomy, bilateral oophorectomy, or bilateral tubal ligation), post-menopausal for at least 12 months (and confirmed with a screening follicle stimulating hormone [FSH] level in the post-menopausal lab range), do not require contraception during the study.
5. Male participants with female partners of childbearing potential must agree to use contraception (e.g., if not vasectomized, should either abstain from sexual intercourse or use a highly reliable method of contraception such as condom and diaphragm with spermicide during intercourse) if they become sexually active during the study or within 90 days following their participation in the study. Male subjects must also not donate sperm during and for 90 days following their participation in the study.
6. Subject is a nonsmoker (for at least 3 months) with negative urinary cotinine test at Screening and agrees to abstain from alcohol, recreational drugs (including marijuana), and tobacco- or nicotine-containing products for the duration of the study.
7. Subject is able to comprehend and is willing to sign an informed consent form and abide by the study restrictions.

Exclusion criteria:

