11.1.2. Sample Size for Assay Sensitivity of C-QTc Analysis

To demonstrate assay sensitivity with C-QTc analysis, it must be shown that the $\Delta\Delta\text{QTcF}$ of a single dose of 400 mg moxifloxacin exceeds 5 msec (i.e., the lower bound of the 2 sided 90% CI of the predicted QTcF effect [$\Delta\Delta\text{QTcF}$] should exceed 5 msec) at the observed geometric mean Cmax of 400 mg moxifloxacin. Under the assumption that the predicted moxifloxacin QTc effect is 10 msec with a SD of ΔQTcF of 8 msec for both oral moxifloxacin and oral placebo, a sample size of 40 evaluable subjects in a crossover of moxifloxacin and placebo will provide at least 81% power to demonstrate assay sensitivity with a 1-sided 0.05 significant level. The power to detect the effect of moxifloxacin on QTc over the entire crossover period is at least 86%. This power is estimated approximately using a 2-sample t-test in nQuery 8 (www.statsols.com). The number of 20 evaluable subjects in each sequence on moxifloxacin (40 over both Day 10 and 16) also agrees with recent recommendations of the FDA, which proposes at least 20 subjects ([Huang 2019](#)).

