4.10.3.3 Assay sensitivity

The moxifloxacin C-QTc model will follow the same methods as described for setmelanotide model from Section 4.10.2.1.1 to 4.10.2.1.4. The sensitivity analysis will be performed separately for day 10 and day 16, due to the different baseline for moxifloxacin in group 2 and 3.

The assay sensitivity will be accepted if the slope for the relationship is significant at the 5% level and if the lower bound of the 90% CI of $\Delta\Delta\text{QTc}$ predicted at moxifloxacin C_{max} is above 5 ms.

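### The per-day power for assay sensitivity is stated as at least 81%, but the plan's own inputs give about 62% with 20 moxifloxacin and 20 placebo subjects.

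*SAP*

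**What the plan says.** Two places attach the figure to a single Holter day. The protocol synopsis (Sample Size Justification) says that 20 evaluable subjects on moxifloxacin and "20 evaluable subjects receiving placebo at each Holter ECG assessment day (Days 10 and 16) will provide at least 81% power". SAP 4.13 repeats this almost word for word: "20 evaluable subjects receiving placebo at each ECG assessment day (Days 10 and 16) will provide at least 81% power". Both set it at a 1-sided 0.05 level, and both contrast it with at least 86% over the whole crossover. Neither gives an effect size or SD.

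Protocol 11.1.2 supplies the inputs: "Under the assumption that the predicted moxifloxacin QTc effect is 10 msec with a SD of" ΔQTcF of 8 msec on both treatments, with the lower bound of the 2-sided 90% CI required to exceed 5 msec. It names the method: "This power is estimated approximately using a 2-sample t-test in nQuery 8". But it ties the 81% to a different unit: "a sample size of 40 evaluable subjects in a crossover of moxifloxacin and placebo will provide at least 81% power". A second figure follows directly: "The power to detect the effect of moxifloxacin on QTc over the entire crossover period is at least 86" percent.

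For the analysis itself, SAP 4.10.3.3 states: "The sensitivity analysis will be performed separately for day 10 and day 16", and gives as its reason: "due to the different baseline for moxifloxacin in group 2 and 3". It also requires a concentration slope significant at the 5% level. Protocol 11.3.2 has only the 5 msec criterion, with no split by day and no slope condition.

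**The concern.** The same 81% is attached to two designs, 20 versus 20 on one day and 40 subjects crossed over, and these cannot have equal power on the same inputs. Protocol 11.1.2 also gives two powers, 81% and 86%, with nothing to show how their inputs differ.

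A finding of no QT effect can be interpreted only if the study shows it could have detected moxifloxacin. Because the SAP tests each day separately, the per-day power is the one that applies; the 86% matches no analysis specified in SAP 4.10.3.3. If the per-day power is overstated, readers will underestimate the risk that assay sensitivity is not shown. That section also leaves open whether one day or both must succeed.

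**Working it through.** **Inputs** (Protocol 11.1.2 unless noted)
- True effect 10 msec and threshold 5 msec, so the distance to detect is 10 − 5 = 5 msec.
- SD of ΔQTcF 8 msec in both arms.
- 1-sided α = 0.05, 2-sample t-test.
- 20 versus 20 per day (synopsis and SAP 4.13).

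**Formula.** Power = 1 − F(t₀.₉₅,ν; ν, δ), where F is the noncentral t distribution function. For two samples of n, SE = SD × √(2/n), ν = 2n − 2 and δ = distance / SE.

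**Step 1: does the method reproduce the plan's other figures?**
- Setmelanotide (Protocol 11.1.1: effect 3, limit 10, SD 8, 20 versus 20): SE = 8 × √0.1 = 2.530, δ = 7 / 2.530 = 2.767, ν = 38. Power 85.8%; stated at least 85%.
- Moxifloxacin crossover, 40 subjects, zero within-subject correlation: SD of the difference = 8√2 = 11.31, SE = 11.31 / √40 = 1.789, δ = 5 / 1.789 = 2.795. Power 86.5% by a paired test (ν = 39) or 87.0% by a 2-sample test at 40 versus 40 (ν = 78); stated at least 86%.

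Both stated floors hold.

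**Step 2: the per-day figure.** SE = 8 × √(2/20) = 2.530, δ = 5 / 2.530 = 1.976, ν = 38. Power **61.6%** (63.0% by the normal approximation); stated at least 81%. The gap is 81 − 61.6 = 19.4 points.

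**Step 3: what would give 81% per day?**
- More subjects: 24 versus 24 (everyone enrolled) gives 68.7%, 33 versus 33 gives 80.7%, and 34 versus 34 gives 81.7%.
- A larger effect, at 20 versus 20 and SD 8:

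| True effect (msec) | Power per day |
|---|---|
| 10 | 61.6% |
| 11 | 75.3% |
| 11.5 | 81.0% |
| 12.5 | 89.7% |
| 15 | 98.7% |

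- A smaller SD: about 6.15 msec at an effect of 10 msec.

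Either rescue (11.5 msec at SD 8, or SD 6.15 at 10 msec) raises the 40-subject crossover to about 97%. That does not breach a floor of 86%, but it means the 81% and 86% were not computed as close floors from one set of inputs.

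**Step 4: effect of the unstated day rule.** With t-test power 0.616 per day and zero correlation between a subject's two days (an assumption):
- both days must pass: 0.616² = 0.38;
- either day suffices: 1 − (1 − 0.616)² = 0.85.

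Simulation with Group 2 on moxifloxacin on Day 10 and Group 3 on Day 16, at an assumed between-day correlation of 0.7, gives 28% (both) and 95% (either). The slope condition is not in any of these figures, and its effect cannot be computed from the documents.

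**The case against.** The arithmetic is not in dispute; the case against is about what it shows.

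- **Imported inputs.** The synopsis and SAP 4.13 give no effect or SD, and Protocol 11.1.2 attaches the 81% to the 40-subject crossover, where it is literally true as a floor. So 81% might rest on unwritten assumptions. That possibility stands. But the synopsis and the SAP plainly contrast each day with the whole crossover, and the documents offer no other inputs.
- **The t-test is only an approximation.** The planned analysis is a mixed concentration-QTc model over many timepoints, which may gain precision. This also stands as a limit. However, the protocol claims that gain only for setmelanotide, does not quantify it, and attributes the 81% to a t-test.
- **The effect may be larger.** Protocol 3.2 expects a peak effect of 10 to 15 msec, and 11.5 msec lies inside that range. But Protocol 11.1.2 fixes 10 msec for the power calculation.
- **The day-rule powers are hypothetical.** No rule or between-day correlation is stated, so those figures show only that the rule matters. An either-day rule would in fact exceed 81%.
- **A SAP may add detail.** Protocol 11.3 calls itself a summary, so the split by day and the slope test need not contradict it. That is fair, and these are secondary to the power figure.
- **Nothing in the design changes.** Protocol 11.1.2 also cites a recommendation of at least 20 subjects, which does not depend on the 81%. Low power makes a failure to show assay sensitivity more likely; it does not create a false demonstration. This bears on the consequence, not on whether the stated figure is right.

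**Conclusion.** The concern holds. On the only inputs the documents give, 20 versus 20 per day has about 62% power, not at least 81%. The method is the plan's own and reproduces its 85% and 86% floors. The synopsis and SAP 4.13 also conflict with Protocol 11.1.2 over which design the 81% describes.

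The 62% assumes a true effect of 10 msec (the low end of the expected range), SD 8 msec and a 2-sample t-test. It excludes any mixed-model gain and the slope condition. The documents cannot show whether 81% is a wrong number or rests on assumptions that were left out; either way the statement needs correcting. The missing day rule and the extra slope condition are real but secondary.

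**What to change.** - **Synopsis and SAP 4.13:** replace the 81% with about 62% per day on the Protocol 11.1.2 inputs, or state the assumptions that give 81%, such as an effect of about 11.5 msec or an SD of about 6.15 msec.
- **Protocol 11.1.2:** remove the 81% from the 40-subject crossover and keep at least 86%.
- **SAP 4.10.3.3:** say whether one day, both days or a combined analysis decides assay sensitivity. Reconcile the slope condition with Protocol 11.3.2, and give the power for the rule chosen.

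One option, not a requirement, is a combined two-day moxifloxacin versus placebo model with treatment coded by subject and day and Day as a fixed term. This differs from Eq. 1 in SAP 4.10.2.1.3, where treatment is set by subject. It would also have to deal with the SAP's stated reason for splitting by day, the different baselines in Groups 2 and 3.

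Cost: no extra subjects. It takes wording changes in three places, with either a less favourable figure or added assumptions, and a short SAP amendment. The combined model, if chosen, needs its own specification and power statement.

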4.14 Changes in the Conduct of the Study or Planned Analysis

Not Applicable.

6 APPENDICES

6.1 Schedule of Assessments

Table 6-1 Schedule of Assessments

Study Period	Screening		Check-In	Baseline	Treatment										Follow-up	Treatment Discontinuation
Study Day Assessment	-28 to -2		-2	-1	1	2-6	7	8	9	10	11-14	15	16	17	23 ± 2	7 ± 4 days after last SC dose
Informed consent	X															
Inclusion/exclusion review	X		X													
Medical history review	X															
Physical exam ^a	X			X										X	X	X
Comprehensive skin exam ^b	X															
Fitzpatrick classification scale	X															
Height and weight ^c	X			X										X	X	X
Vital signs ^d	X			X										X	X	X
Pregnancy test ^e	X			X										X		X
FSH test	X			X												
Urine drug screen	X			X												
CRU confinement			X	X	X	X	X	X	X	X	X	X	X			
CRU discharge														X		
Fasting ^f			X					X				X				
Meal administration ^g				X				X	X	X	X	X	X			

Study Period	Screening		Check-In	Baseline	Treatment										Follow-up	Treatment Discontinuation
Study Day Assessment	-28 to -2		-2	-1	1	2-6	7	8	9	10	11-14	15	16	17	23 ± 2	7 ± 4 days after last SC dose
Setmelanotide administration ^h					X	X	X	X	X	X	X	X	X			
Moxifloxacin administration ⁱ										X			X			
PK sampling ^j										X			X			
Continuous 12-lead ECGs (Holter monitor) ^{k,l}				X						X			X			
Safety 12-lead ECGs ^{l,m}	X				X		X						X	X	X	
Clinical labs ⁿ	X				X		X						X	X	X	
Adverse events	X		←		Continuous				→							X
Concomitant medication review	X		←		Continuous				→							X
C-SSRS ^o	X				X									X		X

CRU = Clinical Research Unit; C-SSRS = Columbia Suicide Severity Rating Scale; ECG = electrocardiogram; FSH = follicle stimulating hormone; INR = international normalized ratio; PK = pharmacokinetic; PT = prothrombin time; PTT (or aPTT) = partial thromboplastin time

^a A full physical exam will be conducted at Screening. A brief physical exam will be conducted at each check-in, study discharge, and follow-up.

^b A comprehensive skin evaluation will be performed by the Investigator at Screening. If any concerning lesions are identified during the screening period, the subject should be referred to a dermatologist for assessment and potential biopsy and results should be confirmed as to whether the lesion is benign prior to first dose of setmelanotide. If the pre-treatment biopsy results are of concern, the subject will be excluded from the study.

^c Height will only be collected at Screening.

^d Supine blood pressure, supine heart rate, pulse rate, and tympanic (ear) body temperature. Heart rate and blood pressure will be measured using the same arm for each reading after the subject has been resting in the supine position for at least 5 minutes. For timepoints at which vital signs, PK blood samples, and/or ECGs are all to be collected, ECGs should be collected first followed by vital signs then PK samples, with the timing of the PK sample to occur at the nominal time.

^e Serum pregnancy test will be performed at Screening. Urine pregnancy test will be performed on all other designated days.

^f On the evening before continuous ECG sampling, subjects will undergo a 10-hour overnight fast.

^g Breakfast is to be administered at approximately 7:00 AM every day in the CRU (30 minutes pre-dose). Lunch, dinner, and a snack will be administered at approximately 12:00 PM (after 4-hour assessments), 6:00 PM (after 10-hour assessments), and 9:00 PM, respectively.

^h **Group 1** will receive SC setmelanotide QD (approximately 7:30 AM) at a dose of 2 mg from Days 1 to 7; 3 mg from Days 8 to 10; 5 mg from Days 11 to 13; and 7 mg from Days 14 to 16.

Groups 2 and 3 will receive SC placebo QD (approximately 7:30 AM) from Days 1 through 16.

All doses will be double-blinded.

ⁱ **Group 1** will receive oral placebo with their SC setmelanotide dose on Days 10 and 16.

Group 2 will receive oral moxifloxacin 400 mg on Day 10 and oral placebo on Day 16.

Group 3 will receive oral placebo on Day 10 and oral moxifloxacin 400 mg on Day 16.

All doses will be double-blinded. On Days 10 and 16, subjects should receive SC setmelanotide/placebo first. Oral moxifloxacin/placebo should then be administered within 2 minutes of the SC dose.

^j Blood samples for quantification of setmelanotide and moxifloxacin concentrations will be collected at pre-dose and 0.5, 1, 1.5, 2, 2.5, 3, 4, 5, 6, 7, 8, 9, 10, 12, 16, and 24 hours post-dose on Days 10 and 16. The PK samples collected at 0.5 hours post-dose will have a sampling window of \pm 2 minutes, samples collected from 1 hour though 2.5 hours post-dose will have a sampling window of \pm 5 minutes, samples collected from 3 hours through 10 hours post-dose will have a sampling window of \pm 10 minutes, and samples collected from 12 through 24 hours postdose will have a sampling window of \pm 20 minutes; however, collection of samples outside of the window will not be considered protocol deviations. The timing of all PK samples should be recorded to the nearest minute. For timepoints at which vital signs, PK blood samples, and/or ECGs are all to be collected, ECGs should be collected first followed by vital signs then PK samples, with the timing of the PK sample to occur at the nominal time.

^k ECGs will be extracted at Day -1 and on Days 10 and 16 at the following timepoints: pre-dose and 0.5, 1, 1.5, 2, 2.5, 3, 4, 5, 6, 7, 8, 9, 10, 12, 16, and 24 hours post-dose. The Day -1 extractions will begin at 7:30 AM (the time of anticipated dosing on Days 10 and 16).

^l For ECG collection, subjects will rest in the supine position for at least 10 minutes before and 5 minutes after each timepoint. For timepoints at which vital, PK blood samples, and/or ECGs are all to be collected, ECGs should be collected first followed by vital signs then PK samples, with the timing of the PK sample to occur at the nominal time.

^m Safety ECGs will be collected at the Screening visit, CRU Baseline (Day -1), final CRU discharge, and the Follow-up visit.

ⁿ Safety clinical laboratory tests will include: hematology with platelet count and standard indices, chemistry panel (includes sodium, potassium, chloride, CO₂, albumin, total protein, glucose, BUN, creatinine, uric acid, AST, ALT, GGT, CPK, alkaline phosphatase, total bilirubin, direct bilirubin, LDH, calcium, phosphorus, magnesium), and urinalysis with microscopic analysis if positive findings on dipsticks warrant further examination. Safety laboratories will also include a coagulation profile (PT or INR, and PTT also referred to as aPTT).

^o In order to be eligible for the study, at Screening, a subject cannot have a suicidal ideation of type 4 or 5, a history of a suicide attempt in the past 20 years, or any suicidal behavior in the last month. If at any time during the study a subject has a suicidal ideation of type 4 or 5, or any suicidal behavior, the subject should be referred to a mental health professional.

Rhythm Pharmaceuticals, Inc.
RM-493-032

Statistical Analysis Plan

Table 6-2 Algorithm for Treatment-Emergent Adverse Events:

Start/Increase Severity Date	Stop Date	Action
Known	Known	Considered as a treatment-emergent adverse event (TEAE) if start date on or after the date of the first dose of investigational product (IP)
	Partial	Considered as a TEAE if start date on or after the date of the first dose of IP. The last day of the month and the last month (ie, December) will be used if the stop day/month is missing.
	Missing	Considered as a TEAE if start date on or after the date of the first dose of IP
Partial, but known components show that it cannot be on or after first IP taken date	Known	Not a TEAE. The first day of the month and January will be used if the start day/month is missing.
	Partial	Not a TEAE. The first day of the month and January will be used if the start day/month is missing. The last day of the month and the last month (ie, December) will be used if the stop day/month is missing.
	Missing	Not a TEAE. The first day of the month and January will be used if the start day/month is missing.
Partial, could be on or after first IP taken date	Known	Considered as TEAE, if stop date is after first IP taken date. The first IP taken date will be used if start date is in the same month/year with first IP taken date, or the first day of the month and January will be used if the start day/month is after first IP taken date Considered as not TEAE, if stop date is prior to first IP taken date. The first day of the month and January will be used if the start day/month is missing.
	Partial	Considered as TEAE. The first IP taken date will be used if start date is in the same month/year with first IP taken date, or the first day of the month and January will be used if the start day/month is after first IP taken date. The last day of the month and the last month (ie, December) will be used if the stop day/month is missing.
	Missing	Considered as TEAE. The first IP taken date will be used if start date is in the same month/year with first IP taken date, or the first day of the month and January will be used if the start day/month is after first IP taken date.
Missing	Known	Considered as TEAE if stop date is on or after the date of the first dose of IP.
	Partial	The last day of the month and the last month (ie, December) will be used if the stop day/month is missing. If the imputed stop date is on or after the first dose of IP considered as a TEAE; if the year is missing, considered as a TEAE
	Missing	Considered as a TEAE

Table 6-3 Algorithm for Prior/Concomitant Medications:

Start Date	Stop Date	Action
Known	Known	If stop date is prior to the date for the first dose of IP, considered as prior; if stop date is on or after the date for the first dose of IP, considered as concomitant.
	Partial	The last day of the month and the last month (ie, December) will be used if the day/month of stop date is missing. If the imputed stop date is prior to the date for the first dose of IP, considered as prior; if the imputed stop date is on or after the date for the first dose of IP, considered as concomitant.
	Missing	Considered as concomitant.
Partial	Known	If stop date is prior to the date for the first dose of IP, considered as prior; If stop date is on or after the date for the first dose of IP, considered as concomitant. The first day of the month and January will be used if the start day/month is missing.
	Partial	The last day of the month and the last month (ie, December) will be used if the day/month of stop date is missing. If the imputed stop date is prior to the date for the first dose of IP, considered as prior; if the imputed stop date is on or after the date for the first dose of IP, considered as concomitant. The first day of the month and January will be used if the start day/month is missing.
	Missing	Considered as concomitant. The first day of the month and January will be used if the start day/month is missing.
Missing	Known	If stop date is prior to the date for the first dose of IP, considered as prior; if stop date is on or after the date for the first dose of IP, considered as concomitant.
	Partial	The last day of the month and the last month (ie, December) will be used if the day/month of stop date is missing. If the imputed stop date is prior to the date for the first dose of IP, considered as prior; if he imputed stop date is on or after the date for the first dose of IP, considered as concomitant.
	Missing	Considered as concomitant.
